7 ETHICS AND REGULATORY REQUIREMENTS

7.1 Confidentiality

In order to observe the confidentiality of personal data, each patient will be allocated a confidential identification code consisting of the investigator site number followed by a 3-digit patient number. CRFs or any other documents submitted to the sponsor will identify the patient by this identification code. Each investigator will maintain a patient identification list which would detail the identification code along with the corresponding patient identifiers (name and date of birth).

Each subject should be numbered in reverse chronological order from 001 as the most recent subject prior to study initiation at the site.

7.2 Waiver of Consent

A waiver of informed consent is key to perform this retrospective chart review study. Informed consent will not be possible to obtain as the care has already been provided by the surgeon/investigator and it is unlikely the patient will return to the surgeon for a clinical visit. In addition, this chart review involves no more than minimal risk to the subjects and the waiver will not affect the rights and welfare of the subjects since care has already been given.

7.3 Waiver of HIPAA Authorization

Waiver of HIPAA authorization is key for the success of this chart review. Not only will it be difficult to obtain the authorization since the care has already been provided by the surgeon/investigator and it is unlikely that the patient will return to the surgeon for a clinical visit, but the use or

disclosure of protected health information involves no more than a minimal risk to the privacy of the individuals.

8 STUDY FINANCES

The study will be funded by Integra Lifesciences Corporation. The Sundt™ internal and external (Loop) Carotid Endarterectomy Shunt is considered a pre-amendment device and is FDA registered under the device listing D024713.

9 RETENTION

Study records must be retained by the Investigator for 2 years following the conclusion/ termination of the study and the publication (if applicable). Study records should not be destroyed without prior written agreement between the Sponsor and the study Investigator. At the completion of the study, details of the archival process must be provided to the Sponsor. Study records are subject to inspection by applicable health and regulatory agencies at any time.

10 PUBLICATION PLAN

A report will be prepared under the responsibility and according to the Integra LifeSciences Corporation SOPs. It will include the study objectives, the methodology, statistical analysis and raw data listings, and the conclusions of the study.

The sponsor is not allowed to use investigator's name in any publication without prior written consent. The investigator is not allowed to use sponsor's name in any publication without prior written consent.

1. LIST OF ABBREVIATIONS

Abbreviation	Term
BMI	Body Mass Index
CFR	Code of Federal Regulations
eCRF	Electronic Case Report Form
EMR	Electronic Medical Records
FDA	Food and Drug Administration
GCP	Good Clinical Practices
ICF	Independent Consent Form
Integra	Integra LifeSciences Corporation
IRB	Institutional Review Board
ITT	Intent-to-Treat
MedDRA	Medical Dictionary for Regulatory Activities
PMCF	Post Market Clinical Follow-up.
PP	Per Protocol
QC	Quality Control
SAE	Serious Adverse Event (As further defined in section 5.1)
SAP	Statistical Analysis Plan
SAS	Statistical Analysis System
SCS	Sundt™ Carotid Shunt
SD	Standard Deviation
SOP	Standard Operating Procedures
SV	Screening Visit
TLA	Transient Ischemic Attack
USA	United States of America

2. INTRODUCTION

This document provides a detailed description of the statistical methods and procedures to be implemented during the analysis of the clinical study. The methods and procedures are intended to support the generation of study report, including detailed descriptions of the populations and methodologies, as well as summary tables, listings and graphics.

This statistical analysis plan (SAP) is based on Version 1.0 of the Protocol# C-SCS-001.

3. STUDY OBJECTIVES

The primary objective of this study to retrospectively investigate the safety and efficacy of the Integra Sundt™ carotid shunt during endarterectomy procedures.

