1.3 Intended Use

The carotid endarterectomy shunts are indicated for temporary carotid artery bypass during carotid endarterectomy procedures in order to help protect the cerebral hemispheres from ischemia during the period of carotid artery occlusion. These shunts are designed as temporary indwelling catheters and are not intended for permanent placement.

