2 OBJECTIVE AND ENPOINTS

2.1 Primary Objective

The primary objective of this study to retrospectively investigate the safety and efficacy of the Integra Sundt™ carotid shunt during endarterectomy procedures.

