6 STATISTICAL ANALYSIS

The PMCF is a retrospective chart review. All analyses will be descriptive in nature. No formal statistical analyses will be performed. The study objectives will be presented by summary statistics.

Summary statistics (mean, standard deviation, quintiles, counts, and percentages) will be presented for all demographic (i.e. age, gender, etc.), clinical baseline characteristics (diagnosis, medical history, medications), surgical procedures (procedures performed, duration of surgery) and complications.

The primary objective will be evaluated by summarizing the incidence of injury to the artery or cerebral ischemia secondary to shunt placement.

All statistical analysis will be conducted using SAS.

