3.1. Primary Study Endpoint

The primary endpoint of this study is evidence of injury to the artery or cerebral ischemia secondary to shunt placement and removal.

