4. STUDY DESIGN

This is a non-randomized, multi-center, single-arm, all-comers retrospective Post Market Clinical Follow-up study investigating subjects who received a Sundt™ carotid shunt during a carotid endarterectomy before study initiation at the site. The study duration from the first patient's chart review to the completion of the last patient's chart review is expected to be 1 year. The study will end when the data for 100 subjects has been collected.

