7. STATISTICAL ANALYSES

7.1. General Statistical Considerations

The PMCF is a retrospective chart review. All analyses will be descriptive in nature. No formal statistical analyses will be performed. The study objectives will be presented by summary statistics.

Summary statistics (mean, standard deviation, quintiles, counts, and percentages) will be presented for all demographic (i.e. age, gender, etc.), clinical baseline characteristics (medical history, surgical history, medications), surgical procedures (procedures performed, duration of surgery) and complications.

The primary objective will be evaluated by summarizing the incidence of injury to the artery or cerebral ischemia secondary to shunt placement.

All statistical analysis will be conducted using SAS[®] for Windows, version 9.4 or later.

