7.2.2. Analysis Populations

7.2.1.1. Efficacy population

Not applicable

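### The objective names efficacy, but a single-arm harm endpoint can describe only safety and device performance, and the primary incidence is planned with no measure of precision

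*SAP*

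**What the plan says.** **Objective.** The Protocol synopsis, Protocol 2.1 and SAP 3 all give the primary objective as to "retrospectively investigate the safety and efficacy of the Integra Sundt™ carotid shunt during endarterectomy procedures".

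**Endpoint.** Protocol 2.2 and SAP 3.1 define one endpoint: "evidence of injury to the artery or cerebral ischemia secondary to shunt placement and removal". There is no second, efficacy-type endpoint.

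**Design.** SAP 4 describes a "non-randomized, multi-center, single-arm, all-comers retrospective Post Market Clinical Follow-up study". Neither document gives a control group, historical rate or performance goal.

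**Populations.** Under SAP 7.2.1.1 the efficacy population is "Not applicable". SAP 7.2.1.2 puts every analysis on the safety population.

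**Analysis.** Protocol 6 states: "All analyses will be descriptive in nature. No formal statistical analyses will be performed". For the endpoint, SAP 7.1 says: "The primary objective will be evaluated by summarizing the incidence of injury to the artery or cerebral ischemia secondary to shunt placement". The statistics listed are means, SDs, quintiles, counts and percentages. No confidence interval appears in either document.

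**Data rules.** Protocol 5.1 enters a silent chart as no on its yes/no questions. SAP 7.2.7 repeats the twelve questions without that rule, and SAP 7.3 bases summaries on non-missing data without imputation.

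**The concern.** The device is indicated to "help protect the cerebral hemispheres from ischemia during the period of carotid artery occlusion" (Protocol 1.3). Efficacy would mean that patients had less ischemia than they would have had without it. A single arm in which everyone was shunted, measured on harm attributed to the shunt, has nothing to set that against. A low event rate reported under an objective that names efficacy could be read as evidence of protection.

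The second issue is how the result will be read. A bare figure such as 0/100 does not show how high a true rate remains compatible with it. Neither document justifies the sample size in terms of precision, so nothing else in the plan tells the reader.

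What the percentage counts is also not fully settled. The endpoint covers placement and removal, while the analysis sentence mentions placement only. The items that feed the composite are not named.

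**Working it through.** **1. Objective against design.**

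| Element | What an efficacy statement needs | What the documents provide |
|---|---|---|
| Endpoint | A measure of benefit | Harm secondary to the shunt (SAP 3.1) |
| Reference | Comparator or benchmark rate | None (SAP 4; Protocol 3) |
| Population | A defined efficacy set | Marked as not applicable (SAP 7.2.1.1) |
| Planned claim | A test or criterion | Disclaimed (Protocol 6; SAP 7.1) |

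None of the four is present. The documents do provide for device performance: Protocol 5.1 and SAP 7.2.7 use that label for their questions.

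**2. Sample size.** Protocol 3.2 and SAP 6 state 100 patients with no event rate, precision target, alpha or power. There is no derivation to reproduce.

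**3. Precision at n = 100.** The exact (Clopper-Pearson) two-sided 95% limits for x events in n patients are:

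- lower = 0.025 quantile of Beta(x, n − x + 1), or 0 when x = 0
- upper = 0.975 quantile of Beta(x + 1, n − x)

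For x = 0 the upper limit reduces to 1 − 0.025^(1/n). At n = 100 this is 1 − 0.025^0.01 = 3.62%. The Wilson upper limit, as a check, is 3.70%.

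The event counts below are illustrative, since the documents give no expected rate. The 95% level is also an assumption.

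| Events in 100 | Exact 95% CI |
|---|---|
| 0 | 0 to 3.62% |
| 1 | 0.03 to 5.45% |
| 2 | 0.24 to 7.04% |
| 3 | 0.62 to 8.52% |
| 5 | 1.64 to 11.28% |

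**4. The denominator may be below 100.** Inclusion criterion 3 requires imaging records, but it sets no time window and does not require a documented neurological exam. The assessment covers up to 60 days (SAP 7.2.6), and SAP 7.3 uses non-missing data. With 0 events and assumed evaluable numbers:

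- n = 80: 1 − 0.025^(1/80) = 4.51%
- n = 60: 1 − 0.025^(1/60) = 5.96%

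**5. The numerator.** SAP 3.1 covers placement and removal; SAP 7.1 covers placement. Question 9 (vessel injury on removal) counts under SAP 3.1, but it is unclear whether it counts under SAP 7.1. Question 10 records post-operative ischemia without asking about attribution, whereas the endpoint requires it to be secondary to the shunt.

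**6. Silent charts.** Questions 10 and 11 correspond to the two components and are yes/no items under the silent-means-no rule. The post-operative assessment (Protocol 5; SAP 7.2.6) lists the same two components separately, outside that rule. The documents do not say which source feeds the primary incidence. For illustration, suppose 3 events and 20 silent charts out of 100. With the rule the result is 3/100 = 3.0% (0.62 to 8.52%). Without it, the result is 3/80 = 3.75% (0.78 to 10.57%).

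**The case against.** **The SAP already contains the efficacy problem.** It has no efficacy population, puts all analysis on safety and disclaims formal testing. The objective says investigate, not demonstrate. This largely stands. A reader might infer that the sponsor plans an efficacy claim, but the documents do not support that. What remains is an objective in SAP 3 that SAP 7.2 does not carry through.

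**Ischemia is what the device is meant to prevent, so its incidence is relevant.** This stands for performance, and the incidence should be reported. Without a comparator or benchmark it still cannot be credited to the shunt.

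**An interval is a preference in an openly descriptive study.** Its absence contradicts nothing in the plan, and a reader given x/n could compute one. But an interval tests no hypothesis, fits a descriptive plan and costs almost nothing.

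**The exact limits assume independent patients.** This is a fair caution. Protocol 3.2 allows three sites of 40, 40 and 20. The size-weighted mean cluster is then (40² + 40² + 20²)/100 = 36. With assumed intraclass correlations of 0.01 and 0.05, the design effects are 1 + 35 × 0.01 = 1.35 and 1 + 35 × 0.05 = 2.75. A rough zero-event upper limit, 1 − 0.025^(design effect/100), is then 4.9% or 9.6%. The documents give no correlation, so this shows direction only.

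**The silent-chart and missing-data rules can be read in sequence.** They can: entry as no first, then summaries of whatever is still missing. A reader might infer a contradiction, but none is shown. The SAP simply does not state the order. The understatement also applies only where Protocol 5.1 items feed the table.

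**Conclusion.** The point holds as a mismatch between the stated objective and what the design can answer, together with a reporting gap on the primary result. The study can describe safety and device performance; it cannot show that the shunt protected patients from ischemia. It does not follow that the planned analysis is wrong or that an efficacy conclusion has been pre-specified.

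The practical size is what a low count would leave open: with no events, a true rate up to about 3.6% at 100 evaluable patients, or about 4.5% to 6.0% at 80 to 60. These figures rest on a two-sided 95% level, independent patients and assumed evaluable numbers; clustering by site would widen them. Correction is advisable because it is cheap and affects how the main result will be read.

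**What to change.** 1. **Objective.** In the synopsis, Protocol 2.1 and SAP 3, replace safety and efficacy with safety and device performance. State in the SAP and the report that no efficacy conclusion will be drawn.
2. **Primary summary (SAP 7.1).** Align the wording with the endpoint so that removal is included; Protocol 6 has the same shorter wording and can be aligned in the same amendment. Name the CRF items that feed the composite and count each patient once. Report the composite and each component as x/n, with the actual evaluable n and an exact (Clopper-Pearson) two-sided 95% CI. Note that the interval assumes independent patients and ignores clustering by site.
3. **Silent charts.** On tables that use Protocol 5.1 yes/no items, and only those, add a footnote that no includes charts silent on the item, so those incidences may be understated. State in SAP 7.3 that the non-missing rule applies after that data-entry rule.

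**Cost.** Short wording amendments to the protocol and SAP, one exact-CI option on existing SAS tables and a footnote. No new CRF field or repeat chart abstraction is needed. The sponsor loses the word efficacy from the objective, and a low event count will carry a visible upper limit. If amending the protocol across up to 10 centers proves burdensome, the statement in the SAP and report that no efficacy conclusion will be drawn secures most of the benefit.

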3.1. Primary Study Endpoint

The primary endpoint of this study is evidence of injury to the artery or cerebral ischemia secondary to shunt placement and removal.

4. STUDY DESIGN

This is a non-randomized, multi-center, single-arm, all-comers retrospective Post Market Clinical Follow-up study investigating subjects who received a Sundt™ carotid shunt during a carotid endarterectomy before study initiation at the site. The study duration from the first patient's chart review to the completion of the last patient's chart review is expected to be 1 year. The study will end when the data for 100 subjects has been collected.

5. STUDY PROCEDURE

This study is a retrospective review of patients who have undergone a carotid endarterectomy procedure with the use of the Sundt™ carotid shunt prior to study initiation.

Eligible subjects for the study should be identified by the 3-digit site number followed by the 3-digit subject ID. Numbering of the subjects should be done in a reverse chronological order with the most recent subject being 001 followed by the second most recent being 002 and so forth.

Required information will be collected through a review of the patient chart or electronic medical records (EMR) by the Principal Investigator or delegated personnel. The delegated staff member shall collect demographics, details surrounding the procedure, and the post-operative assessment.

6. SAMPLE SIZE DETERMINATION

100 patients will be enrolled at up to 10 centers, with up to a maximum of 40 consecutive patients enrolled at each center. Patients will be enrolled at a minimum of 3 centers. This study will take place in the United States only.

7. STATISTICAL ANALYSES

7.1. General Statistical Considerations

The PMCF is a retrospective chart review. All analyses will be descriptive in nature. No formal statistical analyses will be performed. The study objectives will be presented by summary statistics.

Summary statistics (mean, standard deviation, quintiles, counts, and percentages) will be presented for all demographic (i.e. age, gender, etc.), clinical baseline characteristics (medical history, surgical history, medications), surgical procedures (procedures performed, duration of surgery) and complications.

The primary objective will be evaluated by summarizing the incidence of injury to the artery or cerebral ischemia secondary to shunt placement.

All statistical analysis will be conducted using SAS[®] for Windows, version 9.4 or later.

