5 STUDY PROCEDURES

This study is a retrospective review of patients who have undergone a carotid endarterectomy procedure with the use of the Sundt™ carotid shunt prior to study initiation.

Eligible subjects for the study should be identified by the 3-digit site number followed by the 3-digit subject ID. Numbering of the subjects should be done in a reverse chronological order with the most recent subject being 001 followed by the second most recent being 002 and so forth.

Required information will be collected through a review of the patient chart or electronic medical records (EMR) by the Principal Investigator or delegated personnel. The delegated staff

member shall collect demographics, details surrounding the procedure, and the post-operative assessment.

- **Demographics**
 - Age
 - Gender
 - Height
 - Weight
 - Relevant Past Medical History
 - Transient Ischemic Attack (TIA)
 - Stroke
 - Asymptomatic Carotid Stenosis
 - Bleeding Disorder
 - Diabetes
 - Smoking
 - Other relevant past medical history per the investigator's opinion
 - Past Surgical History
 - Previous Head or Neck Surgery
 - Previous Head or Neck Radiation
 - Previous Vascular Surgery
 - Other relevant surgical history per the investigator's opinion
 - Diagnosis / Indication for Surgery
 - Medications
- **Procedure**
 - Date of surgery
 - Procedure(s) performed
 - Duration of surgery
 - Device information, including lot number
 - Medications
 - Any complications noted in the operative report and in the investigator's opinion determined to be related to the device
- **Post-operative Assessment (up to 60 days post-procedure)**
 - Evidence of cerebral ischemia as indicated by post-operative neurological exam
 - Evidence of injury to artery as seen on post-operative imaging of the carotid artery either by carotid duplex ultrasound or angiogram

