5.1 Device Performance

The delegated site staff will collect information regarding the device performance.

The following device performance questions will be part of the case report form and will be collected from the patient medical record including both the operative note and the anesthesia record for the procedure. For the “yes / no” questions below, if the medical record is silent on the answer to the question it will be assumed that the answer is “no”.

1. Was the shunt use routine or selective? If selective, specify the test and the result that led to use of the shunt.
2. Was there any delay in surgery or complication due to preparation of the device for surgery? If yes, please explain.
3. What was the clamping method type for shunt insertion?
4. How long was the carotid artery cross clamped for shunt insertion?
5. Was there any device-related damage to the artery during insertion of the shunt? If yes, please explain.
6. Was there evidence of clot formation within the shunt at any point during the procedure? If yes, describe how this was detected and what was the remedy. What was the impact to the procedure?
7. Was there any evidence of reduced flow within the shunt other than clot formation (e.g. due to kinking, malposition within the artery)?
8. Was there any evidence of excessive bleeding around the shunt after initial placement? If yes, what was the remedy and the result of that remedy?
9. Did removal of the shunt cause vessel injury or complicate closure? If yes, please explain.
10. Was there evidence of post-operative cerebral ischemia noted in the neurological exam?
11. Did the subject experience injury to the artery due to the device as evidenced by the imaging of the carotid artery either by carotid duplex ultrasound or angiogram?
12. Were there any other device-related complications not previously recorded in the case report forms? If yes, please explain.

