7.2.1.2. Safety population

The safety population will consist of the patients who undergone a carotid endarterectomy with the Sundt™ carotid shunt. All analysis will be based on the safety population.

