7.2.6. Post-operative Assessment (up to 60 days post-procedure)

Post-operative assessment will be summarized, details will be listed by subject.

- Evidence of cerebral ischemia as indicated by post-operative neurological exam
- Evidence of injury to artery as seen on post-operative imaging of the carotid artery either by carotid duplex ultrasound or angiogram

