7.3. Missing Data

No imputations is planned for missing data. All summaries will be based on the non-missing data.

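### The primary incidence is reported without a confidence interval, and the rule that answers 'no' for silent records merges undocumented charts with event-free ones

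*SAP*

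**What the plan says.** **Analysis.** SAP 7.1 states: "The primary objective will be evaluated by summarizing the incidence of injury to the artery or cerebral ischemia secondary to shunt placement". Protocol 6 has the same sentence and adds that "The study objectives will be presented by summary statistics". The statistics listed in both places are means, standard deviations, quintiles, counts and percentages. Both sections declare the study descriptive, with no formal analysis.

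**Sample size.** SAP 6 reads: "100 patients will be enrolled at up to 10 centers, with up to a maximum of 40 consecutive patients enrolled at each center". Protocol 3.2 matches it. Neither gives an expected rate or a precision.

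**Silent records.** Protocol 5.1 says of its yes/no device performance questions that "if the medical record is silent on the answer to the question it will be assumed that the answer is" 'no'. Those questions include 5 (arterial damage at insertion), 9 (vessel injury or complicated closure at removal), 10 (post-operative ischemia in the neurological exam) and 11 (arterial injury on imaging). SAP 7.2.7 lists the same twelve questions without the rule. SAP 7.3 plans no imputation and says: "All summaries will be based on the non-missing data". SAP 7.2.1.2 adds: "All analysis will be based on the safety population".

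**A second source for the same outcomes.** The post-operative assessment also collects both components: "Evidence of injury to artery as seen on post-operative imaging of the carotid artery either by carotid duplex ultrasound or angiogram" (Protocol 5) and "Evidence of cerebral ischemia as indicated by post-operative neurological exam" (SAP 7.2.6). No silent-record rule is attached to it.

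**Eligibility.** Inclusion criterion 3 in Protocol 4.1 requires that records of post-operative carotid imaging be available. No criterion requires a documented neurological exam.

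**The concern.** The incidence is the only planned evaluation of an objective that covers safety and efficacy. A bare 0% or 2% from 100 charts does not tell the reader which event rates remain possible.

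The silent-record rule adds a second difficulty. A chart with a documented negative finding and a chart that says nothing both become 'no'. Once stored that way, they cannot be told apart without going back to the charts. The reader then cannot see how much of a low incidence is documented absence of events and how much is absence of documentation.

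Because the endpoint's source items are not named, two programmers could both follow the plan and report different figures. One could use the Protocol 5.1 questions, with silence already converted. The other could use the post-operative assessment items, with silent charts dropped as missing.

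**Working it through.** **Inputs from the documents.** N = 100 (Protocol 3.2, SAP 6); a binary composite endpoint (Protocol 2.2, SAP 3.1); the silent-record rule (Protocol 5.1); summaries on non-missing data (SAP 7.3). No alpha, power, expected rate or precision target is stated, so there is no sample-size figure to reproduce.

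**Assumed inputs.** The event counts x and the number of silent charts s. The documents give neither, so a range is shown.

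**Step 1: precision at 100 charts.** Exact (Clopper-Pearson) two-sided 95% limits, with charts treated as independent:
- lower = 0.025 quantile of Beta(x, n − x + 1), or 0 when x = 0
- upper = 0.975 quantile of Beta(x + 1, n − x)
- for x = 0 the upper limit reduces to 1 − 0.025^(1/n); with n = 100 this is 3.62%

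| Events / charts | Incidence | Exact 95% CI |
|---|---|---|
| 0/100 | 0% | 0–3.6% |
| 2/100 | 2.0% | 0.2–7.0% |
| 5/100 | 5.0% | 1.6–11.3% |

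**Step 2: direction of the silent-record rule.** A silent chart adds 1 to the denominator and 0 to the numerator. If the silence were resolved, the numerator could rise but not fall. The rule therefore lowers the incidence or leaves it unchanged. If silence is unrelated to outcome, the expected reported rate is the true rate × (1 − silent fraction); for example, 5% × (1 − 0.20) = 4%.

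**Step 3: illustration for one component.** Compare x/100 (silence counted as 'no') with x/(100 − s) (documented charts only):

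| x | s (assumed) | Silence = 'no' | Documented only |
|---|---|---|---|
| 0 | 20 | 0% (0–3.6%) | 0/80 = 0% (0–4.5%) |
| 0 | 40 | 0% (0–3.6%) | 0/60 = 0% (0–6.0%) |
| 2 | 20 | 2.0% (0.2–7.0%) | 2/80 = 2.5% (0.3–8.7%) |
| 2 | 40 | 2.0% (0.2–7.0%) | 2/60 = 3.3% (0.4–11.5%) |

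These rows apply to a single component. For the composite, a chart may be documented on one component and silent on the other, so a documented-only denominator needs its own rule.

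**Step 4: where silence can occur.**
- *Question 11 (injury on imaging).* Criterion 3 makes a chart with no imaging record ineligible, so silence is limited. It is not excluded: the criterion sets no time window, and an imaging report may not address injury.
- *Question 10 (ischemia).* If an exam is on file and notes no ischemia, 'no' is the literal answer with or without the rule. The rule matters where no exam is on file, and no entry criterion prevents that.
- *Questions 5 and 9 (injury at insertion and removal).* These depend on the operative record, which criterion 3 does not secure.

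**The case against.** **The study is descriptive and has no benchmark or decision rule, so the missing interval is only a presentation gap.** Much of this stands. A power calculation is not needed and 100 is not shown to be a wrong number. Counts, percentages and subject listings are planned, and a reader given 0/100 could work out 3.6%. But an interval is itself descriptive, and readers should not have to derive the uncertainty of the primary result. Listings do not help with silence once it is stored as 'no'.

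**The 20 and 40 silent charts have no basis in the documents and may be too high.** This stands. They show direction and scale and do not predict what the study will find. Criterion 3 makes such numbers less plausible for imaging.

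**Documented-only rates can be biased too.** This also stands. If surgeons chart positive findings more reliably than negative ones, dropping silent charts pushes the rate up. The documented-only figure belongs in a sensitivity display and should not replace the main summary.

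**A reader might infer that Protocol 5.1 and SAP 7.3 contradict each other.** The documents do not establish that. The two can be read in sequence: silence becomes 'no' at data capture, so nothing is missing for those questions at analysis. What remains is an ambiguity, because the post-operative assessment items carry no such rule and the endpoint's source is not named.

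**Conclusion.** The point holds as a cheap improvement to a valid descriptive plan. Three things are established from the text:
- no interval is planned for the primary incidence;
- the Protocol 5.1 rule counts undocumented charts as event-free on questions 5, 9, 10 and 11;
- neither document names the items that feed the primary endpoint.

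The interval widths are firm, given 100 evaluable charts treated as independent. The direction of the silent-record effect is firm as well. Its size is unknown, because the documents give no silent fraction and no event rate.

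A reader might go further and conclude that the reported incidence will be materially too low, or that both components are equally exposed. The documents support neither. Criterion 3 limits silence on imaging injury, and the remaining exposure lies mainly in question 10 where no neurological exam is on file and in questions 5 and 9 where the operative note says nothing.

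**What to change.** 1. **Intervals and precision.** In SAP 7.1, report the composite and each component as n/N, percentage and exact (Clopper-Pearson) two-sided 95% CI. In SAP 6, state the resulting precision for 100 evaluable charts treated as independent: upper limit 3.6% at 0/100, 0.2–7.0% at 2/100, 1.6–11.3% at 5/100.
2. **Endpoint source.** In SAP 7.1, name the items that feed the primary endpoint (the Protocol 5.1 questions, the post-operative assessment, or both) and state that the Protocol 5.1 rule applies to the main summary. Add a cross-reference in SAP 7.3.
3. **Silence flag.** Keep the 'no' answer that Protocol 5.1 requires. Beside each endpoint item, add a separate CRF flag that distinguishes a silent record from a documented 'no'. Because the answer itself does not change, Protocol 5.1 can stay as written.
4. **Sensitivity display.** Report the number of silent records per component, and the incidence and CI per component among charts documented for that component. For the composite, count a chart as an event if either component is positive, and as a non-event only if both are documented negative. Note that documented-only rates may be biased upward if positive findings are charted more reliably.

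**Cost.** Edits to SAP 6, 7.1 and 7.3, a small CRF change, a few lines of SAS, and a second look at the endpoint items in charts already abstracted. The report will show wider uncertainty than a bare percentage does. No hypothesis test and no larger sample are needed.
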